**Confidential**

## **7. *Statistical Methods***

### **7.1. *Study Subjects***

#### **7.1.1. *Disposition of Subjects***

Number of subject screened enrolled, withdrawal, complete of each pregnancy phase and study will be reported. The number of subjects assigned to CSII/SAP group, with or without sensor will also be provided as overall and for each center.

#### **7.1.2. *Clinical Investigation Plan (CIP) Deviations***

All protocol deviations will be presented in the listings.

#### **7.1.3. *Analysis Sets***

All enrolled subjects who have participated in Orchestra Pregnancy Observational Study in Poland will be included in the efficacy analysis population. All enrolled subjects will be included in the safety analysis population.

### **7.2. *General Methodology***

All data from the time of screening until the end of the study will be collected either on eCRFs or electronically by uploading the various devices. Data and analysis will be summarized in a Clinical Study Report.

No statistically powered analyses or hypothesis testing will be performed. Summary and descriptive statistics will be performed.

### **7.3. *Center Pooling***

Up to 23 investigational centers will be used during this study. Data will be pooled for analysis

### **7.4. *Handling of Missing Data and Dropouts***

No imputation will be used for missing data

### **7.5. *Adjustments for Multiple Comparisons***

Not Applicable.

### **7.6. *Demographic and Other Baseline Characteristics***

Baseline information and demographic characteristics such as age, gender, weight, BMI, diabetes duration, insulin regimen, etc. will be summarized. Medical information such as previous severe hypoglycemia and DKA history up to 12 month prior to study start will also be summarized.

This document is electronically controlled. Printed copies are considered uncontrolled.

**Confidential**

### **7.7. Treatment Characteristics**

Not Applicable

### **7.8. Interim Analyses**

Not Applicable.

### **7.9. Evaluation of Objectives**

#### **▪ Analysis of Primary Objectives**

Descriptive analysis will be performed for all available groups: 1) all enrolled; 2) those who failed to achieve a pregnancy; 3) those who become pregnant after the pre-conception phase; 4) those who already pregnant and enrolled after.

#### **Glycemic control measured by HbA1c**

Calculate descriptive statistics for HbA1c

- A1C and change of A1c
  - from baseline
  - each Pregnancy trimester
- Proportion of subjects achieving A1C < 6% (6.5%, 7%, 7.5%, 8%)

#### **Glycemic Control measured by Continuous Glucose Monitoring Data (for subjects with available sensor data (SG) only)**

Calculate descriptive statistics for Sensor glucose distribution , the following variables will be analyzed as overall and stratified by pregnancy outcome (no conception, delivery, miscarriage, etc.) and completeness of treatment phase (complete follow-up, pregnancy and 6 weeks after delivery, pre-conception phase only, etc.)

- Mean SG per subject per day
- SG variation (CV, SD, MAGE) per subject per day
- % of SG < 50mg/dL, 50-60mg/dL, 60-70mg/dL, 70-120mg/dL, 120-140mg/dL, 140-180mg/dL, 180-250mg/dL and > 250mg/dL per subject per day
- AUC of SG < 50mg/dL, < 60mg/dL, < 70mg/dL, > 140mg/dL, >180mg/dL and > 250mg/dL per
- Pregnancy trimester
- Duration of treatment received
- Sensor compliance (% of time sensor wear) in SAP group only

This document is electronically controlled. Printed copies are considered uncontrolled.

**Confidential**

The analysis will be repeated for listed variables based on 2-hour postprandial CGM data and night only (10pm to 7am) data.

### **Glycemic Control measured by SMBG Data**

Calculate descriptive statistics for SMBG distribution, the following variables will be analyzed as overall and stratified by pregnancy outcome (no conception, delivery, miscarriage, etc.) and completeness of treatment phase (complete follow-up, pregnancy and 6 weeks after delivery, pre-conception phase only, etc.)

- N, Mean, Median, SD, Min and Max per subject per day per
- Pregnancy trimester
- Duration of treatment received

## ▪ ***Analysis of Secondary Objectives***

### **Pregnancy Outcomes**

Calculate incidence rates for the following events as overall and by duration of treatment received.

- Mode of Delivery
  - Normal
  - Elective CS
  - Emergency CS
- Preterm Delivery (< 37 weeks)
- Miscarriage (< 22 weeks or >= 22 weeks)
- Neonatal Morbidity
  - Neonatal Hypoglycaemia
  - Other
- Other Pregnancy Related Serious Adverse Events

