The minimum number of subjects to be enrolled is 100 women with complete follow-up of pregnancy from pre-conception until 6 weeks after delivery. Based on local data and experience, complete follow-up from the pre-conception phase will be possible for about 1/3 of the pregnancies. In about 2/3 of the cases, CSII will start during the first trimester of pregnancy, at the latest on the 16th week.

The expected total sample size is therefore 500 subjects including

- 100 subjects with complete follow-up – all phases on CSII, including SAP (pre-conception, pregnancy, 6 weeks after delivery).
- 300 subjects with pregnancy (enrollment up to the 16th week of pregnancy) and 6 weeks after delivery
- 100 subject with early termination (for various reasons like miscarriage, no conception within 12 months, etc.)

Enrollment will stop when data from 100 pregnancies with complete follow-up from pre-conception until 6 weeks after delivery have been collected.

C.7 Number of investigation sites and study duration

The Orchestra Foundation identified up to 30 sites in Poland to which they decided to make the pump donation (See the attached list, Annex L2.2).

The expected minimum number of subjects per investigation site is 2, the maximum number is 70. The numbers of subjects from the particular sites are based on the geography, potential, and level of experience of the site.

The time period for enrollment is 30 months, and started in May 2013. The treatment period is up to 22 months depending on in which phase of pregnancy the subject is enrolled. Data is collected at the beginning, during and at the end of the treatment period. Final report of the study is expected in 2018.

Table 1: Timelines of the study

| Project /Task | Start | End |
|---|----------------------------------|----------------------------------|
| Clinical study | Nov 2012 | Dec 2017 |
| 
 • Kick-off • Enrollment • End of study | Nov 2012 May 2013 Feb 2017 | Nov 2012 Dec 2015 Dec 2017 |
| Data | May 2013 | Dec 2017 |
| 
 • Data collection • • • Preliminary results • Data processing | May 2013 2017 Dec 2017 | Dec 2017 2017 Feb 2018 |
| Publication | Early 2018 | End 2018 |

D SUBJECT SELECTION

D.1 Inclusion criteria

A subject is eligible for the study if the following criteria are met:

1. Female diagnosed with Diabetes Mellitus Type 1

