| Table 2 : Procedures and Data Collection at each visit | | | | | | | | | |
|---|-------------------------|-----------------------|-------------------------|---------------------|-------------------------|-------------------------|----------------|------------------------|---|
| Visit number | Visit 1 - Preconception | Visit 2a * | Visit 2b ** | Visit 1 - Pregnancy | Visit 3 | Visit 4 | Visit 5 *** | Visit 6 | Premature end of study |
| Visit type | Physical visit | Physical visit | Physical visit | Physical visit | Physical visit | Physical visit | Physical visit | Physical visit | Physical visit |
| Target study visit | Preconception planning | 12 weeks ammenorrhoea | 12 months | Pregnancy | 24 weeks of amenorrhoea | 36 weeks of amenorrhoea | Delivery | 6 weeks after delivery | At any time point (e.g. miscarriage, early dropout) |
| Tolerance window for the visit | | (± 4 weeks) | (± 2 weeks) | | (± 2 weeks) | (± 2 weeks) | (+ 2 weeks) | (± 2weeks) | |
| Procedures | | | | | | | | | |
| Patient Informed Consent | X | | | X | | | | | |
| Inclusion/exclusion criteria | X | | | X | | | | | |
| Assign Patient ID number | X | | | X | | | | | |
| Ask patient to complete HFS questionnaire | X | | X | X | X | X | | X | |
| Ask patient to complete DTSQs | X | | X | X | X | X | | X | |
| Ask patient to complete DTSQc | | | | | X | | | | |
| Complete eCRF - demographic and clinical characteristics | X | | | X | | | | | |
| Create Carelink Clinical account | X | | | X | | | | | |
| Upload data from insulin pump into CareLink Clinical | | X | X | | X | X | X | X | |
| Upload compatible BG meter into CareLink Clinical | | X | X | | X | X | X | X | |
| Check if patient is properly trained on Devices | X | | | X | | | | | |
| Record distributed devices in CRF and device tracking log | X | | | X | | | | | |
| Distribute supplies | X | X | | X | X | X | X | | |
| Complete follow-up eCRF | | X | x | | X | X | X | X | |
| Collect Serious Adverse Events | | X | X | | X | X | X | X | X |
| End of study eCRF | | | in case of no pregnancy | | | | | | X |
| Return of devices | | | in case of no pregnancy | | | | | X | X (early dropout) |
| * If patient is already pregnant at the time of enrollment, follow pcedures under 'Visit 1 - Pregnancy' | | | | | | | | | |
| ** Visit 2b is not applicable for women who became pregnant within 6 months of follow-up | | | | | | | | | |
| *** Data collection in eCRF in two weeks or during 'Visit 6' | | | | | | | | | |

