## **5. Investigation Plan**

### **Study design:**

The project is designed as a multi-center prospective observational Post-Market-Release study to be conducted in up to 30 centers in Poland.

Total duration of the study per patient will be up to 22 months (up to 12 months pre-conception phase, pregnancy, and 6 weeks after delivery). The optimal study start is the beginning of pre-conception phase, however, pregnant women up to the 16th week of pregnancy can participate in the study too. The study end is 6 weeks after delivery. If conception does not occur within 12-months, the patient's study participation is terminated, and the insulin pump might be taken away from the patient. The following therapy is decided by the investigator. If the pump is not taken away after the 12-month of trial period for conception, the patient can continue insulin pump therapy until the pump is needed for another patient.

The study started in May 2013; enrolment period is planned for 30 months which can be modified by the decision of the Steering Committee. The final report will be available within 24 months after the end of enrolment.. Data collection will be stopped when data have been collected from 100 pregnancies with complete follow-up (including pre-conception phase, pregnancy, delivery and 6 weeks of lactation).

This document is electronically controlled. Printed copies are considered uncontrolled.

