#### **Visit 6 – 6 weeks after delivery ( $\pm$ 2 weeks window)**

- Ask patient to complete the HFS and DTSQs questionnaires
- Weigh the patient
- Measure the patient's blood pressure
- Collect the patient's medical data listed in the relevant eCRF
- Fill in the eCRF and submit the data
- Upload data into CareLink Clinical from the insulin pump (and BG meter, if applicable)
- Terminate pump therapy

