### **Neonatal Outcomes**

Calculate descriptive statistics for the following as overall and by duration of treatment received.

- Respiratory Distress
  - 1 and 5 minute Apgar scores
- Infant Birth Weight

This document is electronically controlled. Printed copies are considered uncontrolled.

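### Pregnancy outcomes are to be split by length of treatment; if that means elapsed pump or study time, the outcome helps set its own stratum and miscarriage and preterm rates differ with no pump effect

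*SAP*

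**What the plan says.** SAP 7.9, Pregnancy Outcomes, states: "Calculate incidence rates for the following events as overall and by duration of treatment received". Neonatal Outcomes, covering Apgar scores and birth weight, states: "Calculate descriptive statistics for the following as overall and by duration of treatment received". Protocol H.1.2 has the same instructions. No time origin, end point, cut-points or denominator is given in the readable text.

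Other places bear on what the clock would be:
- Protocol C.7: "The treatment period is up to 22 months depending on in which phase of pregnancy the subject is enrolled".
- Protocol C.6, for about two thirds of cases: "CSII will start during the first trimester of pregnancy, at the latest on the 16th week".
- SAP 5, Study design: "The study end is 6 weeks after delivery". The Visit 6 list ends with "Terminate pump therapy".
- Protocol F.3, Table 2 times the premature-end visit as "At any time point (e.g. miscarriage, early dropout").
- SAP 5, Treatment, lets a woman keep the pump for 3 more months after a miscarriage.
- For sensor glucose, SAP 7.9 lists treatment duration separately from "completeness of treatment phase (complete follow-up, pregnancy and 6 weeks after delivery, pre-conception phase only, etc".
- SAP 1, Version History, lists sensor-glucose tables by pump time. It lists the delivery-mode and miscarriage/preterm tables as overall, enrolled before pregnancy and enrolled during pregnancy.

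**The concern.** Preterm delivery and miscarriage are both defined by gestational age at the event. If treatment duration is time on the pump or in the study, it runs to the event plus a fixed interval. An early event then shortens the duration under which it is counted. The effect is direct for miscarriage and preterm delivery. For mode of delivery, Apgar and neonatal morbidity it acts only through gestational age, and it should be weaker for birth-weight scores standardised for gestational age. The frequency tables for neonatal hypoglycaemia treatment, neonatal care admission and feeding are not stated to be by duration and are not in question.

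A secondary objective (SAP 4) is to assess potential benefits on neonatal outcomes, and SAP 5 lists preterm delivery and miscarriage under that heading. A table with more losses and preterm births at short duration could be taken as evidence for longer pump use when it shows only how the strata were formed.

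**Working it through.** **The plan's own clock.** At 4.348 weeks per month, 12 months + (38 + 6)/4.348 = 22.1 months, counting 38 weeks from conception. With 40 weeks of amenorrhoea it is 22.6. The stated maximum of 22 months is therefore elapsed time ending 6 weeks after delivery.

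**Bound from the documents.** For women followed to the final visit, duration = gestational age at birth − start week + 6.
- Shortest duration for a term birth: 37 − 16 + 6 = 27 weeks, or 37 − 16 + 4 = 25 at the early edge of the 2-week window.
- Loss before week 22, start in pregnancy, later pump time not counted: under 22 weeks.
- A cut-point between 22 and 25 weeks thus puts every such loss, and no term birth, in the short group.
- At the nominal visit time, a birth with duration below 26 weeks occurs before week 26 − 6 + 16 = 36, so it is preterm by construction.

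**Simulation with no pump effect** (2,000,000 conceptions). From the documents: 37% preterm (background figure in SAP 3), one third starting before conception (SAP 6), latest start week 16, clock ending 6 weeks after birth. Assumed:
- miscarriage in 15% of conceptions, at 5 weeks plus an exponential time of mean 5 weeks, truncated at week 22;
- gestational age at birth normal, SD 2 weeks, mean 37 + 0.332 × 2 = 37.7;
- pregnancy starts uniform over weeks 5–16, in women still pregnant;
- pre-conception starts uniform over the preceding 12 months.

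Results by tertile of duration, shortest / middle / longest:

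| Women | Miscarriage, % | Preterm, % of deliveries |
|---|---|---|
| All, clock stops at loss | 20 / 2 / 6 | 52 / 26 / 35 |
| All, 13 weeks of pump time after loss counted | 16 / 3 / 10 | 52 / 25 / 36 |
| Started in pregnancy | 19 / 0 / 0 | 60 / 37 / 18 |
| Started before conception | 40 / 5 / 0 | 43 / 37 / 34 |

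Within each start group the rates never rise with duration. Pooled, they are not monotone, because the longest tertile is mostly pre-conception starters.

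**Sensitivity.**
- True preterm rate 20%: pooled 31 / 12 / 19%.
- Tertiles cut among deliveries only, starts from week 6: the short group is 48–55% for SDs of 1.5–2.5 weeks. With 25% pre-conception starters (100 of 400, SAP 6) the pattern is 54 / 29 / 28%.
- Other loss timings: pooled miscarriage 16–26 / 2 / 6–8%.
- Fixed bands with pregnancies as denominator: preterm is 8–45% below 6 months against 34–36% at 6–9 months. With 10% dropout it is 4–19% against 33–36%, so the direction reverses.

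**By start group, same assumptions.** Preterm is 37% in both groups. Crude miscarriage is 15% in pre-conception starters and about 6% in pregnancy entrants (5–10% over the loss timings tried), because women who lose a pregnancy early never enter. Conditioning on being pregnant at week w removes this: with S(w) the share of losses after w, the risk is 0.15 × S(w)/(1 − 0.15 × (1 − S(w))) in both groups. At week 8 this is 0.15 × 0.465/0.920 = 7.6% for early losses (mean 4 weeks) and 0.15 × 0.824/0.974 = 12.7% for losses uniform over weeks 5–22.

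**The case against.** The strongest reply is that elapsed time is not what is meant for these outcomes. The Version History names pump time only for sensor-glucose tables. The delivery-mode and miscarriage/preterm tables are titled overall and by enrolment group, which parallels the instruction in SAP 7.9. The BMI and albumin/creatinine tables, governed by the same term, are also titled by enrolment group, and no SMBG table is listed by pump time. The C.7 sentence ties the treatment period to the phase at enrolment, which fits that reading too. The table shells in SAP 10 are not visible and may settle it.

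Much of this stands, and it makes the finding conditional. It does not remove it. The instruction as written asks for duration, the plain meaning of which is time, and the same item for sensor glucose appears to correspond to the pump-time tables. Someone following the text of SAP 7.9 would produce the distorted strata.

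Two further points also stand. The study is descriptive (SAP 7.2). And the pooled pattern is not a clean gradient, so a misleading claim of benefit is possible rather than certain.

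A reader might infer that the plan will produce false evidence of benefit from longer pump use. The documents do not support that: the stratifier is undefined, the listed titles point elsewhere, and the direction of the distortion depends on choices not yet stated.

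**Conclusion.** The wording should be changed. If duration means elapsed pump or study time, miscarriage and preterm rates by duration differ with no pump effect. The bounds of 27 (or 25) and 22 weeks follow from the plan's own figures, for women followed to the final visit and with pump time after a loss not counted. The simulated sizes rest on assumed miscarriage rate and timing, spread of gestational age, start times and cut-points; the existence of a difference appeared in every setting tried, its direction and size did not stay fixed.

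If enrolment group is meant, preterm delivery is not distorted and the text only needs aligning with the listed tables. Crude miscarriage would still differ between groups, through late entry, which is a separate mechanism. Overall rates are unaffected and no error rate is involved. Confidence is medium because the shells cannot be read.

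**What to change.** In SAP 7.9 and Protocol H.1.2, for pregnancy outcomes, Apgar and birth weight, replace the duration split with a split by pump-start timing: enrolled before conception or enrolled during pregnancy, optionally with gestational week at start. This is fixed before the outcome and matches the listed tables. Do not tabulate these outcomes by elapsed duration; if such a table is kept, state its clock, cut-points and denominator and label it as not interpretable as an effect of duration.

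For miscarriage, label crude rates by enrolment group as affected by late entry. Add a delayed-entry estimate as a supportive analysis, with each woman at risk only from her gestational week at enrolment and risk-set sizes shown.

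The cost is wording, table shells and a derived variable. The eCRF lists in Protocol F.3 show no explicit pump-start date, so it would come from enrolment or device-upload dates. Gestational week at entry can be worked back from delivery or miscarriage data, but is not clearly available for women who drop out while pregnant, which is why the delayed-entry estimate should be supportive only. It is also imprecise early: with 300 pregnancy entrants uniform over weeks 6–16, about 300 × 2/10 = 60 have entered by week 8, and the simulated standard error is 2.4–3.4 percentage points per group. Start timing is not randomised, so differences stay confounded by who plans a pregnancy.

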### **Neonatal Outcomes**

Calculate descriptive statistics for the following as overall and by duration of treatment received.

- Respiratory Distress
  - 1 and 5 minute Apgar scores
- Infant Birth Weight

This document is electronically controlled. Printed copies are considered uncontrolled.

**Confidential**

- SD scores
- Customised birth weight percentile (LGA, SGA)

Provide frequency tables for the following variables

- Neonatal Morbidity
  - Treatment for Neonatal Hypoglycaemia
- Neonatal Care Admission
  - Duration of Stay
  - Level of Care
- Feeding at Hospital Discharge
  - Breast
  - Bottle
  - Both

### **Questionnaire and Surveys**

The questionnaire and survey results will be presents and by time of questionnaire/survey collected

- Hypoglycaemia Fear Survey (HFS)
- Diabetes Treatment Satisfaction Questionnaire
  - DTSQs
  - DTSQc

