**Confidential**

affects between 25-40% mothers and is three to five times as frequent in early pregnancy as in the period prior to pregnancy. Rates of SH in the late first and early second trimester showed an increase of 16%, and in an intensively treated group subjects had 15 times more SH than the conventionally treated group. Nocturnal hypoglycaemia is also common in the first trimester, with a 37% prevalence shown by hourly venous sampling between 22:00h-07:00h. Ironically, during pregnancy, hypoglycaemia is less harmful to the fetus than to the mother, but hyperglycaemia poses increased risks for the fetus. Therefore, from the perspective of fetal outcomes, strict metabolic control in early pregnancy must still be advocated, but other means for preventing severe hypoglycaemia should be implemented.

CSII in non-pregnant Type 1 subjects was associated with a reduced rate of severe hypoglycaemia without adversely affecting glycaemic control when compared with MDI therapy. There is recent convincing evidence from multicenter randomised controlled trials (RCT) that both CSII and continuous glucose monitoring (CGM) independently, or in combination as sensor-augmented pump therapy (SAP) improve glycaemic control by decreasing HbA1c in the range of -0.43% to -1.2%. An RCT of 71 pregnancies complicated with diabetes had an end-of-pregnancy improvement of -0.6% and reduced risk of macrosomia when using CGM.

Postprandial blood glucose levels have a stronger association with incidence of macrosomia than HbA1c. Two RCTs found that monitoring of post-prandial glucose levels produced better outcomes than pre-prandial monitoring. Neonatal outcomes are more closely associated with hyperglycaemic excursions than with the average glycaemic control. The frequency, magnitude and duration of hyperglycaemic excursions, are best captured by CGM which has an accuracy comparable to gold standard plasma glucose measurements in pregnancy yet provides continuous information on glucose levels. Indeed, analysis of CGM for hyperglycaemia may be a useful marker of anticipated neonatal outcomes.

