### **Secondary objectives:**

- To assess the prevalence of pregnancy complications (rates of preterm delivery, infant birth weight, neonatal care admissions) from preconception phase, throughout pregnancy, during delivery and after delivery during lactation phase (up to 6 weeks)
- To report and assess the potential benefits of CSII, including SAP, on neonatal outcomes
- To evaluate change in patient-reported outcomes using the Hypoglycemia Fear Survey (HFS) and the Diabetes Treatment Satisfaction Questionnaire (DTSQs and DTSQc)

---

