### Maternal outcomes

- HbA1c (local laboratory) – last value before insulin pump therapy started (retrospective value from patient's medical file), 2-3 values during pregnancy, and one value at the end of the study.
- Proportion of women achieving HbA1c <6.0%, 6.5%, 7%, 7.5% and 8% at each trimester
- Serious adverse events
  - Severe hypoglycaemia (according to the standard definition requiring third party assistance – see point F 5. 1) from the period of 12 months prior to study start until study end
  - DKA from the period of 12 months prior to study start until study end
  - Miscarriage, hospitalization because of uterine bleeding, hospitalization because of instable glycaemia and others
  - Any hospital admission
- Weight, BMI
- Daily insulin use
- Medical information: Microalbumin excretion with albumin/creatinin ratio, blood pressure, parity, folic acid and any other supplementation, White classification, diabetes duration, previous insulin regimen
- Number of SMBG/day (patient self-reported)
- Patient questionnaires:
  - Hypoglycaemia Fear Survey (HFS) collected at enrollment, 2-3 x during pregnancy, and 6 weeks after delivery
  - Diabetes Treatment Satisfaction Questionnaire (DTSQs, status version), collected at enrollment, 2-3 x during pregnancy, and 6 weeks after delivery, and Diabetes Treatment Satisfaction Questionnaire (DTSQc, change version), collected at 24 weeks into pregnancy
- Device Data:
  - Descriptive statistics for SMBG and SG (mean, SD, median, min and max)
  - time spent SG < 50 mg/dL
  - time spent SG between 50-70 mg/dL

This document is electronically controlled. Printed copies are considered uncontrolled.

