**Confidential**

## 6. Determination of Sample Size

The minimum number of subjects to be enrolled is 100 women with complete follow-up of pregnancy from pre-conception until 6 weeks after delivery. Based on local data and experience, complete follow-up from the pre-conception phase will be possible for about 1/3 of the pregnancies. In about 2/3 of the cases, CSII will start during the first trimester of pregnancy, at the latest on the 16th week.

The expected total sample size is therefore 500 subjects including

- 100 subjects with complete follow-up – all phases on CSII, including SAP (pre-conception, pregnancy, 6 weeks after delivery).
- 300 subjects with pregnancy (enrollment up to the 16th week of pregnancy) and 6 weeks after delivery
- 100 subject with early termination (for various reasons like miscarriage, no conception within 12 months, etc.)

Enrollment will stop when data from 100 pregnancies with complete follow-up from pre-conception until 6 weeks after delivery have been collected.

This document is electronically controlled. Printed copies are considered uncontrolled.

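### HFS and DTSQs: the visible text of SAP 7.9 has no split by enrolment route and no within-woman change, so a pooled change could not be separated from stage of pregnancy

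*SAP*

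**What the plan says.** SAP section 4 sets the secondary objective: "To evaluate change in patient-reported outcomes using the Hypoglycemia Fear Survey (HFS) and the Diabetes Treatment Satisfaction Questionnaire (DTSQs and DTSQc". The endpoint list in SAP section 5 gives one starting label for both enrolment routes: "Hypoglycaemia Fear Survey (HFS) collected at enrollment, 2-3 x during pregnancy, and 6 weeks after delivery". The procedures show that this label covers two stages. Visit 1a comes before a planned pregnancy, and Visit 1b comes at any time in pregnancy up to week 16. HFS and DTSQs are completed at both.

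For analysis, SAP 7.9 (Questionnaire and Surveys) says: "The questionnaire and survey results will be presents and by time of questionnaire/survey collected". Protocol H.1.2 has the same sentence. The enrolment groups, including "3) those who become pregnant after the pre-conception phase; 4) those who already pregnant and enrolled after", are defined under the primary objectives and are not repeated for the questionnaires.

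In protocol Table 2 the HFS row reads "Ask patient to complete HFS questionnaire | X | | X | X | X | X | | X". The blank after the first mark is Visit 2a (week 12 ± 4 weeks). Women enrolled before conception therefore give no HFS score between enrolment and week 24, and the DTSQs row is the same.

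The SAP introduction says severe hypoglycaemia "is three to five times as frequent in early pregnancy as in the period prior to pregnancy".

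**The concern.** The objective is change, but the visible rule describes a summary at each time point. Two problems follow if it is applied as written.

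First, an enrolment mean can mix pre-pregnancy and early-pregnancy scores. By the plan's own account the risk of the feared event differs several-fold between those stages. For HFS, the distance from such a mean to week 24 or 36 depends partly on how many women entered by each route and on what fear of hypoglycaemia does over pregnancy.

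Second, time-point means describe different women. Enrolment includes those who later stop, later visits do not, and SAP 7.4 excludes imputation.

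The first problem rests on the hypoglycaemia background and so concerns HFS. For DTSQs the documents give no comparable reason for satisfaction to shift in early pregnancy, so the concern there is only mixed starting points and changing sets of women. At stake is a table that readers would take as the answer to the change objective although it cannot support that reading.

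**Working it through.** **Inputs.** SAP section 6 and protocol C.6 plan 100 women with complete follow-up from pre-conception, "300 subjects with pregnancy (enrollment up to the 16"th week) followed to 6 weeks after delivery, and 100 early terminations of unstated route. The severe hypoglycaemia ratio of 3 to 5 is from the SAP introduction. Neither document gives a mean or SD for HFS or DTSQs, so every SD figure below is an assumption.

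**1. The plan's own total.** 100 + 300 + 100 = 500, as stated. (The accompanying remark that about 1/3 of pregnancies are followed from pre-conception does not match 100/400 = 25%. This does not affect the point.)

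**2. Share of enrolment scores from pregnant women.** Let x be the number of early terminations who enrolled in pregnancy, from 0 to 100. Then w = (300 + x)/500.
- x = 0: w = 300/500 = 60%.
- x = 100: w = 400/500 = 80%.
- Among the 400 followed through: 300/400 = 75%.

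**3. Are the starting points comparable for HFS?** Set the pre-pregnancy frequency of severe hypoglycaemia to 1 and the early-pregnancy frequency to k. If Visit 1b women are at the early-pregnancy frequency, the mixed enrolment sample has (1 − w) + w·k.
- k = 3: 0.4 + 0.6×3 = 2.2, up to 0.2 + 0.8×3 = 2.6.
- k = 5: 0.4 + 0.6×5 = 3.4, up to 0.2 + 0.8×5 = 4.2.

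The mixed value matches neither route. This is event frequency, not HFS score; the documents do not give the link between them.

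**4. Pooled HFS change with no pump effect.** Let d be the early-pregnancy excess in HFS over the pre-pregnancy level, in SD, and r the share of d still present at the later visit. The enrolment mean is w·d and the later mean is r·d, so the pooled change is (r − w)·d. Take d = 0.2 to 0.4 (assumed).
- Excess resolves (r = 0): −0.6×0.2 = −0.12 SD to −0.8×0.4 = −0.32 SD.
- Excess persists (r = 1): (1 − 0.8)×0.2 = +0.04 SD to (1 − 0.6)×0.4 = +0.16 SD.

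The sign depends on r, which is unknown. For scale, the 95% half-width of a mean change with n = 400 and an assumed SD of change of 1 is 1.96/√400 = 0.098 SD.

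**5. Changing sets of women alone.** If the routes differed by a constant d and nobody changed, moving from w to 75% shifts the mean by (0.75 − w)·d. With d = 0.4 this is (0.75 − 0.80)×0.4 = −0.02 SD to (0.75 − 0.60)×0.4 = +0.06 SD. This is the smaller effect.

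**6. What a split does.** With d = 0.4, r = 0 and no pump effect, pre-conception entrants show 0.00 SD and pregnancy entrants −0.40 SD; the pooled table shows −0.24 to −0.32 SD. The split removes the mixing. It does not remove the −0.40 SD, which is confounding with the course of pregnancy.

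**The case against.** The strongest reply is that pooling is inferred. The SAP 7.9 sentence is garbled and may have lost a clause. Protocol Table 2 has separate Visit 1 columns for pre-conception and pregnancy, so time of collection could mean two starting points. The SAP version history records that a Questionnaire and Surveys section was added, and the appendix shells cannot be seen. The body text also names no route split for delivery mode or BMI, yet the version history lists separate tables by route for both. This stands: a reader might infer that scores are certainly pooled and reported by collection time alone, but the documents support only that the visible text specifies nothing more.

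A reader might also infer that Visit 1b falls at the peak of risk and week 24 after it. The documents do not show this. The introduction compares early pregnancy with the time before it, documents no decline by week 24, and mentions an increase in the late first and early second trimester. Visit 1b has no lower week limit.

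The DTSQc at week 24 is a direct change measure for satisfaction, so within-woman change is not wholly absent there. HFS has no equivalent.

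Finally, the study is descriptive and without a comparator, so some confounding is inherent. That is true, but it does not excuse leaving change undefined when change is the objective. Table 2 is a visit schedule, not an analysis rule.

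**Conclusion.** The concern holds in a limited form. As far as the visible text specifies, HFS and DTSQs are summarised by collection time, without route or paired change. Such summaries can mix two starting points that are not comparable for HFS, with 60–80% of enrolment scores coming from pregnant women. A pooled change could not be separated from stage of pregnancy.

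The size and sign are unknown. The apparent fall of 0.12–0.32 SD rests on an assumed excess of 0.2–0.4 SD that resolves; if it persists, the result is an apparent rise of 0.04–0.16 SD. A reader might go further and conclude that later change reflects pregnancy and not the pump. The documents do not support that: the two are confounded, and nothing shows that the pump contributes nothing. The argument from hypoglycaemia frequency should not be extended to DTSQs.

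The change is worth making because the study already records the route, the SAP already uses it elsewhere, and the secondary objective otherwise has no interpretable analysis.

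**What to change.** In SAP 7.9, Questionnaire and Surveys:

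1. Tabulate HFS, DTSQs and DTSQc separately for women enrolled before conception and during pregnancy, as the SAP's table list already does for BMI and delivery mode. Label the Visit 1b score as early pregnancy.
2. For HFS and DTSQs, report within-woman change from the first score in women with both scores, with N at each visit.
3. State that change in either route is confounded with the course of pregnancy and cannot be attributed to the pump, and that only the pre-conception route has a non-pregnant starting value.

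If the appendix shells already contain the split, the text need only say so and add items 2 and 3.

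The cost is a few lines of text and no new data. The pre-conception table would have about 100 women with paired scores, giving a 95% half-width of 1.96/√100 = 0.196 SD under the same assumed SD of change, against 0.098 SD for 400. Questionnaires at Visit 2a would give both routes an early-pregnancy score, but they are not part of the required change.
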